1.0 Objectives

22.1 Study Objectives

Describe the purpose, specific aims or objectives. State the hypotheses to be tested.

The purpose of this study is to test the efficacy of virtual reality videos to facilitate exposure therapy in social anxiety disorder (SAD). The exposure therapy videos are the focus of this experiment. Essentially, we are testing the efficacy of the Virtual Reality Exposure Therapy (VRET) scripts (i.e., virtual scenarios, people, and interactions that we expose socially anxious people to). To this end, the goal of the current study is to help people with social anxiety overcome their phobias. Individuals who experience a difficult time building social relationships, accomplishing everyday tasks, or pursuing interviews can practice those same behaviors in a controlled environment.

The study hypotheses are as follows:

1. Virtual reality exposure therapy intervention (vs. waitlist control condition) is effective for treating SAD symptoms.
2. Participants who received the virtual reality exposure therapy will experience maintenance of treatment gains following 3-month and 6-month post-termination of treatment.
3. Users of the virtual reality exposure therapy will demonstrate high amounts of acceptability of the treatment.

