7.0 Study Design and Procedures

7.1 Study Design

Describe and explain the study design.

We will compare exposure therapy via virtual reality technology to a waitlist control group across 8 to 10 sessions with follow-up assessments after 3-month and 6-month post-termination of treatment.

NOTE: While research procedures may be carried out in the Psych Clinic, no data will be entered into a medical record/student health record. Therefore, this data is strictly research data – it would not fall under the HIPAA or FERPA regulations.

Further, involvement in this study will not have any impact of participants' treatment options. Participants may seek other forms of professional mental healthcare elsewhere outside the context of clinical research during the course of this study.

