7.2 Study Procedures

Provide a description of all research procedures being performed and when they are being performed (broken out by visit, if applicable), including procedures being performed to monitor participants for safety or minimize risks. Include any long-term follow-up procedures and data collection, if applicable.

Describe where or how you will be obtaining information about participants (e.g., medical records, school records, surveys, interview questions, focus group topics, audio or video recordings, data collection forms, and collection of specimens through invasive or non-invasive procedures to include the amount to be collected and how often). Add any data collection instruments that will be seen by participants to your study in CATS IRB (<http://irb.psu.edu>) in the “Supporting Documents” page.

Step 1: Phone Screening

Potential participants will first complete a brief phone screen to ensure they meet the basic criteria for the study. During the phone screen, the participant will be asked to provide a brief description of their presenting problem, as well as some basic information about their age to ensure they meet some of the inclusion criteria for the study (over the age of 18 and seeking help for social anxiety treatment).

Researchers will administer the script before scheduling the initial assessment (see “LIMBIX – Screening Consent - Phone.docx” under recruitment materials).

Step 2: Initial Assessment

Those that appear to meet some of the criteria based on the phone screen will be scheduled for an in-person initial assessment. The waiting period between the initial phone screen and appointment for the baseline assessment will depend on the availability of the participant and study team member conducting the baseline assessment.

During the initial assessment visit, participants will review the study consent with a study team member (“LIMBIX - Baseline Assessment Script” done online). Once consent is obtained, participants will be instructed to complete the baseline self-report questionnaires using a tablet or computer in one of the clinic or laboratory rooms at the Moore building, which will link to the Qualtrics questionnaires. The self-report assessments will take approximately 40 minutes.

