During the session, some research personnel will assist with helping participants to respond if the participants have problems responding to the system (“LIMBIX - Scripts - RA Prompts If Participant Gets Stuck.docx”).

Step 5: Between-Session Symptom Assessment

To monitor treatment progress, participants will complete between-session symptom assessments at the end of each session (“LIMBIX - Measure - Between session symptom assessments.pdf”). Participants will also be asked to engage in practice of skills they learn in treatment between sessions (refer to “LIMBIX – Between-Session Homework”).

This applies to participants in the treatment, but not waitlist, condition. For participants placed on the waitlist, this applies only once treatment has started.

Step 6: Termination

The research therapist will work with participants to determine therapy goals at the start of treatment, and will work with them to monitor progress on these goals throughout treatment. Generally, treatment length will span 8 to 10 sessions, depending on the participant’s symptoms, response to treatment, and therapists’ clinical judgment.

Step 7: Final Assessments

Participants will be asked to complete the follow-up questionnaire packet (see “LIMBIX - Measure - Follow-up questionnaire packet.pdf”). This packet will be provided to them prior to their final session, and the final interview (conducted online “LIMBIX - Measure - Final interview.pdf”) will be included in the termination session. The final interview session will be administered at the end of Session 10.

Three and six months after treatment, participants will be contacted online to complete the 3-month and 6-month follow-up questionnaires (see “LIMBIX - Measure - 3-month post-treatment.pdf” and “LIMBIX - Measure - 6-month post-treatment.pdf” accordingly). At this time, participants will only complete self-report measures online.

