7.3 Duration of Participation

Describe the duration of an individual subject’s participation in the study.

We determined the length of time needed to complete the assessments. Based on this, it is predicted that the baseline assessments will be completed in 90 minutes, and the assessments at the end of treatment and 3- and 6-month post should take between 30 minutes to complete. In addition to time spent on assessments, participants will attend 8 to 10 sessions of weekly therapy sessions that will each be 50 minutes long. Note that the between-session measures are done at the end of each session. The frequency of treatment sessions will be determined by the participant's presenting concerns, but the following presents a reasonable estimate for most clients with social anxiety disorder who meet the study eligibility criteria.

Initial visit assessments:	60 minutes
3- month post-treatment assessments:	15 minutes
6- month post-treatment assessments:	15 minutes
8-10 treatment sessions:	$50 \times 10 = 500$ minutes
Final visit assessments:	10 minutes
Total time (approximate):	600 minutes

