8.3 Statistical methods

Describe the statistical methods (or non-statistical methods of analysis) that will be employed.

We will conduct a series of growth curve analyses to test for treatment efficacy. We will use the R packages 'lme4' (Bates, Maechler, & Bolker, 2012), 'lmerTest' (Kuznetsova & Brockhoff, 2014), and 'lavaan' (Rosseel, 2012) to calculate the growth trajectories for each participants. We will test for the impact of time using participants' scores at post-treatment, and at 6-month and 12-month follow-ups. We intend to perform separate models for each of the study outcome measures.

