14.0 Subject Stipend (Compensation) and/or Travel Reimbursements

Describe the amount and timing of any subject stipend/payment or travel reimbursement here. If there is no subject stipend/payment or travel reimbursement, indicate as not applicable.

If course credit or extra credit is offered to participants, describe the amount of credit and the available alternatives. Alternatives should be equal in time and effort to the amount of course or extra credit offered.

If an existing, approved student subject pool will be used to enroll participants, please indicate as such and indicate that course credit will be given and alternatives will be offered as per the approved subject pool procedures.

The following compensation mechanism will be used for all participants: Participants will be awarded a \$40 gift card which will be reimbursed online via email within a week after they have completed the measures at 6-month follow-up. The planned payment is appropriate and mutually beneficial. It maximizes the chances that participants will engage fully with treatment to benefit themselves and complete all of the study procedures. Participants are expected to spend about 10 hours to complete the assessment batteries and therapy sessions. The money is reasonable in compensating their time. However, given that they are also receiving free treatment, we do not compensate them for time spent in therapy or homework from therapy. Further, this amount is not expected to cause undue coercion on the prospective research participants to partake in the study.

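### The growth-curve analysis uses a 12-month visit that is never scheduled and names neither the 3-month visit nor baseline

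*Combined protocol and SAP*

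**What the plan says.** Section 8.3 (Statistical methods) proposes growth curve models to test treatment efficacy, one model per outcome measure. The impact of time is to be tested with "scores at post-treatment, and at 6-month and 12-month follow-ups". The section names no other occasion and states no time coding, baseline term or condition term.

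The rest of the protocol gives a different schedule:

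- Section 22.1, Hypothesis 2, concerns "maintenance of treatment gains following 3-month and 6-month post-termination of treatment".
- Section 7.1 describes 8 to 10 sessions "with follow-up assessments after 3-month and 6-month post-termination of treatment".
- Section 7.2, Step 7: "Three and six months after treatment, participants will be contacted online to complete the 3-month and 6-month follow-up questionnaires".
- Section 7.3: "the assessments at the end of treatment and 3- and 6-month post should take between 30 minutes to complete".
- Section 14.0 sends the gift card "within a week after they have completed the measures at 6-month follow-up".

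Pre-treatment scores are collected: under section 7.2, Step 2, "participants will be instructed to complete the baseline self-report questionnaires". There are also in-therapy scores: under Step 5, "participants will complete between-session symptom assessments at the end of each session", and section 11.0 adds a weekly Beck Anxiety Inventory (BAI). Apart from section 8.3, the quantitative plan consists of the descriptive statistics mentioned in section 22.2.

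**The concern.** There are two linked problems.

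First, the analysis lists a visit that the trial does not hold and leaves out one that a hypothesis needs. Followed literally, it has data at post-treatment and 6 months only, and the 3-month part of Hypothesis 2 is not analysed.

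Second, the models are meant to test efficacy, yet all the named scores come at or after the end of therapy. If baseline is not the reference, the time effect cannot show whether symptoms fell during therapy.

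No other text fixes the occasions for an inferential analysis. The analyst would therefore choose the time points and the reference, possibly after seeing the data, and that choice can change the sign of the time effect.

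**Working it through.** The plan has no calculated figure to reproduce here. The check compares occasions, then asks what each reading of section 8.3 can estimate.

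**1. Occasions side by side**

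| Occasion | Scheduled? | Named in 8.3 as written | Named if 8.3 meant 3 and 6 months |
|---|---|---|---|
| Baseline | Yes (7.2, Step 2) | No | No |
| Post-treatment | Yes (7.2, Step 7) | Yes | Yes |
| 3 months | Yes (22.1, 7.1, 7.2, 7.3) | No | Yes |
| 6 months | Yes (22.1, 7.1, 7.2, 7.3, 14.0) | Yes | Yes |
| 12 months | No | Yes | No |

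As written, 2 of the 4 scheduled packets are named; on the slip reading, 3 of 4. The itemised time in section 7.3 is 60 + 15 + 15 + 500 + 10 = 600 minutes, equal to its stated total, with no 12-month item. The only one-year follow-up mentioned, in section 2.2, belongs to a cited earlier study.

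**2. Could 12 months be counted from baseline?** Time from baseline to the last visit = wait + scheduling lag + weekly sessions + 26 weeks. The wait is 0 or 8 weeks and there are 8 to 10 sessions (section 7.2). A lag of 0 to 3 weeks is assumed.

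- Immediate arm: 0 + 0 + 8 + 26 = 34 weeks, up to 0 + 3 + 10 + 26 = 39 weeks.
- Waitlist arm: 8 + 0 + 8 + 26 = 42 weeks, up to 8 + 3 + 10 + 26 = 47 weeks.

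Over this range the last visit always comes before week 52, so this reading does not rescue the text.

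**3. What the literal reading leaves.** Two occasions at common nominal times give 2 variances + 1 covariance = 3 moments. A random intercept and slope model with residual error has 4 such parameters: two variances, their covariance and the residual variance. Individual trajectories, which section 8.3 sets out to calculate, cannot be separated from residual error. A simpler two-point change model could be fitted, but it is not the one described.

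**4. What a time effect from post-treatment onward measures.** The documents give no outcome means, so these are assumed for illustration, at assumed months 0, 2, 5 and 8.

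| Quantity | Partial relapse: 60, 40, 45, 50 | Gains held: 60, 40, 40, 40 |
|---|---|---|
| Change during therapy | 40 − 60 = −20 | −20 |
| Baseline to 6 months | 50 − 60 = −10 | −20 |
| Slope, post-treatment to 6 months | (50 − 40)/6 = +1.67 per month | 0 |
| Single line through all four | −26.25/36.75 = −0.71 per month | −75/36.75 = −2.04 per month |

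The single-line slope is the sum of cross-products of time and score about their means, divided by the sum of squares of time about its mean (3.75 months), which is 36.75. Adding the 3-month score leaves the post-treatment slope at +1.67 or 0, because the assumed follow-up means lie on a straight line. The literal and slip readings therefore agree.

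Adding baseline is not enough by itself. In the first example one straight line declines by 0.71 points per month while follow-up scores rise by 1.67. Varying the assumed baseline-to-post interval from 1.75 to 4.5 months moves the single-line slopes from −0.67 to −0.90 and from −2.04 to −1.87. The post-treatment slopes do not move.

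**The case against.** The best defence is that section 8.3 does not exclude baseline. Its first sentences promise growth curves for efficacy, and the sentence on the impact of time could be only the maintenance test for Hypothesis 2. Scores from post-treatment onward are right for that test, and a slope of 0 is what maintained gains should give. This stands as a limit: the point about baseline is conditional. But on this reading the 3-month visit is still missing, the 12-month visit still does not exist, and no occasions are stated for the efficacy model.

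Other objections stand in part:

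- The means and times in the example are invented. They show what the estimand leaves out, not the size of any bias in this trial. The supported size is the count of occasions.
- The time budget in section 7.3 is weak evidence. Its total is called approximate, and its prose (90 minutes at baseline, 30 later) disagrees with its list (60, then 10, 15 and 15). Neither version contains a 12-month item, and the other sections suffice without it.
- The session scores and weekly BAI are described as monitoring, so their absence from section 8.3 is not an error.
- Several sections agree on 3 and 6 months, so a wording slip is likely. The documents do not settle this, and the slip reading still leaves baseline unnamed.

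**Conclusion.** The concern holds. One of the three occasions named in section 8.3 has no scheduled assessment, and two of the four scheduled packets are not named. This rests on the text alone and needs no assumption. The 3-month part of Hypothesis 2 is left out of the analysis as written.

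The further conclusion, that the time effect says nothing about improvement during therapy, depends on baseline not being an implied reference. If it is implied, the plan has to say so. The slopes of +1.67, 0, −0.71 and −2.04 rest on assumed means and times and only illustrate the logic.

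The contradiction sits in the plan's only inferential analysis, so it should be corrected before any outcome data are analysed.

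**What to change.** First decide whether the 12-month visit is a slip or an intended visit missing from the schedule, and make sections 22.1, 7.1, 7.2, 7.3, 8.3 and 14.0 agree. If the existing schedule stands, section 8.3 could read:

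> Scores at baseline, post-treatment, 3 months and 6 months will be modelled for each outcome. Time will be coded, piecewise or as categories, so that change from baseline to post-treatment is estimated separately from change from post-treatment to 6 months. Both will be estimated within each randomised condition.

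Other time codings would serve if they keep the two periods apart; one straight line through all four occasions does not. Estimation within condition matters because, for waitlist participants, baseline to post-treatment also spans the 8-week wait. Session-level scores may be added to describe change during therapy, but this is optional.

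Before adopting the text, confirm that the four packets carry the same outcome scales. On that condition the cost is one paragraph, with no added visit or participant. If a 12-month visit was really intended, it must be added to the schedule, which costs a further assessment per participant.

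This change restores within-arm change and the maintenance analysis. It does not make Hypothesis 1 testable against the waitlist, because no end-of-wait score is described; that is a separate issue. Until it is resolved, conclusions from this model should be limited to within-arm change and maintenance.

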22.2 Primary Study Endpoints

State the primary endpoints to be measured in the study. Clinical trials typically have a primary objective or endpoint. Additional objectives and endpoints are secondary. The endpoints (or outcomes), determined for each study subject, are the quantitative measurements required by the objectives. Measuring the selected endpoints is the goal of a trial (examples: response rate and survival).

To answer these questions, the proposed study will use both qualitative and quantitative methods. Qualitative methods will include a semi-structured interview at the end of the study to gather information on the participant's experience, as well as data collected throughout the therapy process. Quantitatively, the study proposes to use basic descriptive statistics to examine treatment outcomes and engagement with digital tools.

This exploratory study will answer the following questions:

- 1) Compared to the waitlist control condition, is the virtual reality exposure intervention more effective for treating symptoms of social anxiety disorder?
- 2) Are there higher treatment gains maintained over time among participants who receive the virtual reality exposure therapy compared to the waitlist control condition?

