8.2 Sample size determination

If applicable, provide a justification of the sample size outlined in section 8.1 – to include reflections on, or calculations of, the power of the study.

The proposed study is focused on examining the efficacy, acceptability, feasibility, and the experience of the patient when using virtual reality in treating job interview phobia. The number of participants (300 per intervention condition; 300 General Social Skills Training; 300 Job Interview Phobia; 150 Waitlist Control) was based on Kampmann et al. (2016) who conducted a virtual reality study with adults with social phobia and used similar primary outcome measures. In their study, their power calculations estimated that 300 participants/per intervention group would be sufficient to find significant differences (two sided-power, power= 80%, alpha -0.05, G*Power 3.2) based on an effect size of exposure therapy found in a meta-analysis (Powers et al., 2008).

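### No primary outcome, contrast or time point is named and section 8.3 fits a separate efficacy model per outcome with no multiplicity rule, so no pre-specified result decides Hypothesis 1

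*Combined protocol and SAP*

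**What the plan says.** Section 22.1 states Hypothesis 1: "Virtual reality exposure therapy intervention (vs. waitlist control condition) is effective for treating SAD symptoms". Section 22.2, the primary endpoint section, turns it into two questions. The first asks whether, against waitlist, "is the virtual reality exposure intervention more effective for treating symptoms of social anxiety disorder". The second asks "Are there higher treatment gains maintained over time among participants who receive the virtual reality exposure therapy compared to the waitlist control condition". Neither names an instrument, a summary measure or a time point, and no other section designates a primary outcome. The questions are introduced with "This exploratory study will answer the following questions", and for the quantitative analysis the same section says "the study proposes to use basic descriptive statistics to examine treatment outcomes and engagement with digital tools".

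Section 8.3 plans growth-curve models whose stated aim is to test efficacy, and adds: "We intend to perform separate models for each of the study outcome measures". It gives no list of outcomes, significance level, testing order or adjustment, and does not say how many models must be positive. The effect it describes is that of time; no treatment or treatment-by-time term appears.

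Section 8.2 gives the groups as "300 General Social Skills Training; 300 Job Interview Phobia; 150 Waitlist Control" and reports a cited study's power calculation at 80% and two-sided 0.05. Section 22.4.3 also randomises to two modules or waitlist, whereas 22.1, 22.2, 7.1 and Step 2 of 7.2 speak of a single VRET condition.

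The instruments named elsewhere have other roles: the SPDQ and BDI-II for subject-pool screening (4.1), the BAI for symptom monitoring and stopping (11.0), and others for usability, cybersickness, negative effects and in-session distress. None is called an efficacy outcome. The questionnaire packets cited in 7.2 are attachments whose contents are not shown.

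**The concern.** A hypothesis of efficacy needs one result, fixed in advance, that decides it. Here the primary endpoint section promises description, which cannot settle a comparison with waitlist, and the analysis section promises one model per outcome without ranking them. If the models disagree, the plan does not say which one counts. A positive finding on one scale among several could be reported as support for Hypothesis 1, and nothing in the plan would rule that out.

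Two things are at stake. The 0.05 level behind the sample size would not apply to the efficacy claim. The 80% power statement would also have no defined test attached to it, because power belongs to a specified outcome and contrast.

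**Working it through.** **Inputs**
- Number of outcomes, K: not in the documents. Assumed 3 to 5, with 1 and 2 shown for reference.
- Level: two-sided 0.05, from the power calculation reported in 8.2. Section 8.3 states none, so its use for each model is an assumption.
- Correlation between outcomes: not in the documents. Shown at 0, 0.5 and 0.8.
- Group sizes: 300, 300 and 150, from 8.2.

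**1. The plan's own figure.** Section 8.2 gives 300 per intervention group but no numerical effect size, so the figure can be neither reproduced nor refuted. What can be computed is the standardised difference detectable with 80% power, d = (1.960 + 0.842) × √(1/n₁ + 1/n₂):
- 300 v 300: 2.802 × 0.0816 = 0.229
- 300 v 150, one module v waitlist: 2.802 × 0.1000 = 0.280
- 600 v 150, pooled VRET v waitlist: 2.802 × 0.0913 = 0.256

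Each figure holds for one test of one outcome.

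**2. One VRET-v-waitlist comparison, K outcomes.** With independent outcomes the chance of at least one false positive is 1 − 0.95^K. For K = 3 this is 1 − 0.857 = 14.3%; for K = 5 it is 1 − 0.774 = 22.6%. Correlated cases were simulated (300,000 draws, equicorrelated normal statistics, absolute z above 1.96).

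| Outcomes | Correlation 0 | 0.5 | 0.8 |
|---|---|---|---|
| 1 | 5.0% | 5.0% | 5.0% |
| 2 | 9.8% | 9.1% | 7.9% |
| 3 | 14.3% | 12.6% | 9.8% |
| 4 | 18.5% | 15.6% | 11.4% |
| 5 | 22.6% | 18.3% | 12.7% |

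**3. Only results that favour VRET.** Counting z above 1.96 in that direction alone, the rates at correlation 0, 0.5 and 0.8 are 7.3%, 6.3% and 4.9% for three outcomes, and 11.9%, 9.1% and 6.4% for five. The nominal rate is then 2.5%, so the relative inflation is similar: 4.9/2.5 = 2.0 at the low end (9.8/5.0 = 2.0 in step 2) and 11.9/2.5 = 4.8 at the high end (22.6/5.0 = 4.5).

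**4. If the modules were tested separately.** The two module contrasts share the waitlist and correlate at (1/150)/(1/300 + 1/150) = 0.667. Two-sided, one outcome gives about 8.5%. At outcome correlation 0.5, three outcomes give 20.7% and five give 29.3%. These figures apply only if such tests are run.

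**5. What was not counted.** Under Step 2 of 7.2 the waitlist group is invited to start treatment after 8 weeks. The randomised comparison with untreated participants ends there, so follow-up times were not counted as further VRET-v-waitlist tests.

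**6. Cost of splitting the level instead.** Bonferroni over four tests at 300 v 150 raises the detectable d from 0.280 to 0.334; at d = 0.28, power falls from 80% to 62%. A single pooled test avoids this loss.

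**The case against.** The strongest reply is that the plan calls itself exploratory and never says that one positive model is enough. Silence on a decision rule is a gap, not a rule. Section 8.3 also sets no level, and Hypothesis 1, the first question in 22.2 and the design statement in 7.1 each describe a single contrast, VRET against waitlist.

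Much of this stands, and it rules out some stronger readings:
- A reader might infer that the plan lets efficacy be declared from any positive model. No section says so.
- A reader might infer that the false-positive rate is several times 5%. The documents give neither the number of outcomes nor their correlation, and with two outcomes the multiple is only 1.6 to 2.
- A reader might infer that separate module tests are planned. The plan has three groups but does not say whether the modules are pooled or tested separately.
- A reader might infer that the SPDQ is the natural primary scale. The documents use it only to screen the subject pool (4.1, 16.2) and do not place it in the baseline or outcome packets.

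The exploratory label does not remove the point. Section 22.1 states hypotheses, 8.3 says the models test efficacy, and 8.2 justifies 750 participants by power at 0.05. The unseen packets do not remove it either: they would show which scales are collected, but the primary one has to be designated in 22.2 or 8.3, and both are present and silent.

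**Conclusion.** The concern holds as a gap in pre-specification. No outcome, contrast or time point is primary, each outcome gets its own model, and nothing controls multiplicity, so no planned result decides Hypothesis 1.

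The size is conditional. With 3 to 5 outcomes each tested at two-sided 0.05, at least one false positive would occur about 10% to 23% of the time for one comparison (correlation 0.8 to 0). Counting only results favouring VRET, it would be about 5% to 12% against a nominal 2.5%. Separate module tests would raise these figures. The outcome count, the correlation and the level per model are all assumptions. That the rate exceeds nominal for any claim resting on the best of two or more outcomes does not depend on their exact values, unless the outcomes are perfectly correlated.

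The missing treatment term in 8.3 has to be repaired at the same time, since a time effect alone cannot answer a question about VRET against waitlist.

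**What to change.** In 22.2 and 8.3, name one primary test:
- **Contrast:** pooled VRET v waitlist, written as a treatment or treatment-by-time term, two-sided 0.05.
- **Outcome:** one social-anxiety severity scale that the sponsor confirms is collected in both groups.
- **Time:** baseline and the end of the 8-week wait, before waitlist participants start treatment.

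Test each module against waitlist at 0.05 only if the pooled test is positive. If neither module has an effect, the pooled effect is null too, so the gate holds the error at 5%; if only one module has no effect, only one false module claim is possible. Section 22.4.3 randomises participants to a module, while Step 3 of 7.2 matches the module to interests and presenting problem. These must be reconciled before a module comparison can be read as randomised.

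Report all other outcomes with Holm adjustment, or as exploratory with 95% intervals. In 22.2, replace descriptive statistics as the efficacy analysis.

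The cost is more than wording. Secondary p-values become less favourable. No section schedules a waitlist assessment at the end of the wait: between-session measures begin only with treatment, and the final packet is tied to the last session. If none is already taken, the existing self-report questionnaire must be given online at that point. Because treatment runs 8 to 10 weekly sessions, the sponsor should also confirm that VRET participants have a score on the same scale at the matching time.
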